Non-Interventional Study (NIS) ProtocolNIS Name/CodeD7913C00070Edition NumberFinal 3.0Date

A diagnostic Study of European and Japanese advanced NSCLC patients to evaluate suitable sample types for EGFR testing: The ASSESS Study

Sponsor:

AstraZeneca AB, [name]

A diagnostic Study of European and Japanese advanced NSCLC patients to evaluate suitable sample types for EGFR testing: The ASSESS Study

Medicinal Products (type, dose, mode of administration) and concomitant medication

The assignment of a subject to a particular therapeutic strategy is not decided in advance by a protocol but falls within current practice and marketing authorisation.

Study Rationale

This study will be conducted in Japan and Europe and will assess the concordance of *EGFR* mutation status derived from tumour samples and blood based circulating free DNA. The data generated will inform the use of less-invasive sample types in diagnostic practice. The study also aims to assess the current status of *EGFR* mutation testing across Japan and Europe and gaps in currently available data including *EGFR* mutation frequency in particular populations and demographic subgroups, *EGFR* mutation frequency in histological subtypes of NSCLC, *EGFR* mutation test process and methodology, utility of multiple sample types in the assessment of *EGFR* mutation status, and impact of *EGFR* mutation testing process, ensuring that patients have access to testing and are treated appropriately on the basis of the molecular features of their disease.

Study Objectives

(a) Primary objective

To determine the level of concordance between *EGFR* mutation status obtained via tissue/cytology and blood (plasma) based testing.

- (b) Secondary objectives
- 1. To determine the *EGFR* mutation frequency (including mutation subtypes) in patients with advanced NSCLC (aNSCLC) of adenocarcinoma and non-adenocarcinoma histologies.
- 2. To describe first line therapy choice following *EGFR* mutation testing.
- 3. To describe second line therapy choice following discontinuation of first line treatment for patients confirmed as *EGFR* mutation positive via tissue/cytology.
- 4. To summarise *EGFR* mutation testing practices in terms of methods, sample types, success rate, mutation detection rate, testing turnaround time and reasons for not testing.
- 5. To determine the correlation between *EGFR* mutation status from tumour and demographic data and disease status.

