2.1 Overall study design

This is a non-interventional diagnostic, international, multicenter and non-comparative study of *EGFR* mutation status in aNSCLC patients (locally advanced and/or metastatic disease) with adenocarcinoma and non-adenocarcinoma histologies.

Approximately 1300 (1000 in Europe and 300 in Japan) aNSCLC patients who fulfil the inclusion/exclusion criteria will be recruited by the investigational sites throughout Europe and Japan. Participating countries from Europe will be: France, Germany, Italy, Spain, Netherlands, UK and Sweden.

Patients will be recruited over approximately 18 months.

It will be mandatory for every enrolled patient to provide a diagnostic tumour sample (i.e. biopsy, cytology or other sample type containing tumour cells) and a diagnostic blood (plasma) sample upon inclusion to be tested for *EGFR* mutations.

Once each patient has signed and dated the informed consent on enrolment, the patient demographics will be recorded and a blood (plasma) sample will be collected.

The tumour sample which was used to diagnose NSCLC will undergo *EGFR* mutation testing according to local practices. The plasma sample will be transported to a designated testing laboratory for *EGFR* mutation testing.

Optional collection of material from the diagnostic tumour sample will be requested from all patients to assess the exploratory objective. Samples will be used to investigate biomarkers which may help define molecular features of NSCLC (e.g. KRAS, EML4-ALK) as an exploratory objective. Biomarker prevalence, co-occurrence and correlation with demographic data will be investigated.

The first line therapy choice will be recorded for all patients. The second line therapy choice will be recorded following discontinuation of first line treatment, only for patients confirmed as *EGFR* mutation positive via tissue/cytology, where applicable.

Assignment of a subject to a particular therapeutic strategy is not decided in advance by this protocol. Medicinal products will be used according to current practice and marketing authorisation.

A Non-Interventional Study is a study in which no additional diagnostic or monitoring procedures shall be applied to the patients.

Table 1: Study plan

Visit description	Screening/enrolment Day -28 to 0	Post EGFR Testing Data
	,	C
		When data
		becomes available
Main study informed consent (including tumour and plasma	Х	
sample EGFR analysis)	Λ	
Inclusion / Exclusion criteria	Х	

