7.2 Secondary variables

The following data will be collected in order to fulfil the secondary objectives of the study:

Patient demographics	• Gender		
	• Age		
	• Race		
	EthnicityWHO Performance status		
	• Smoking status:		
	• Intensity (cigarettes per day)		
	o Duration (years)		
	• Time since cessation (years)		
	• Disease status:		
	 Date of first diagnosis 		
	 Histological type 		
	• TNM (AJCC) disease stage		
	(Edition 7)		
	• Number of organs with		
	metastasis		
	• Location of		
	metastasis/metastases		
1 st -line treatment decision after testing	• Name of treatment		
	• Treatment start date		
	• Reason for treatment choice (including		
and 1. () 1. () ()	Clinical Trial enrolment)		
2 nd -line treatment decision (for patients	• Name of treatment		
confirmed as EGFR mutation-positive via	• Treatment start date		
tissue/cytology)	• Reason for treatment choice (including		
	Clinical Trial enrolment)		
EGFR mutation testing endpoints	• Test result		
	• Overall mutation result (positive		
	negative, unknown)*		
	• Mutation subtype		
	 Testing methodology Sample time and envilopility 		
	• Sample type and availability		
	 Testing turnaround time Basson(a) for testing not being 		
	 Reason(s) for testing not being performed 		
Footnote:	performed		

Footnote:

Smoking is a multi-dimensional phenomenon with many characteristics, such as intensity (in cigarettes per day), duration (in years) and time since cessation (in years). In this study, every patient should report the all information list above to determine the smoking status.

- Deletion, substitution, and/or insertion mutations of tyrosine kinase domain of the *EGFR* gene will be identified and recorded in the CRF. Methods used for measuring *EGFR* mutation status should also be recorded.

*EGFR mutation status will be recorded for each patient as:

- Positive: *EGFR* mutation detected (one or more individual mutations)
- Negative: EGFR mutation not detected
- Unknown: *EGFR* mutation status not determined as *EGFR* mutation positive or *EGFR* mutation negative

It is accepted that mutation assays (methods and individual mutation assays) may differ between labs and institutions. Thus a patient can be positive or negative depending on the method used. As a minimum, laboratories should assess the common *EGFR* mutations: Exon 19 deletions, and Exon 21 L858R point mutations.

Mutation subtypes will also be recorded:

- Exon 18:
 - o G719C/S/A
 - 0 other
- Exon 19:
 - o deletions
 - o other

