- Exon 20:
 - o T790M
 - o insertions
 - o other
- Exon 21:
 - o S768I
 - o L858R
 - o L861Q
 - o Other

The following outcome variables will be calculated in order to fulfil the secondary objectives of the study:

EGFR Testing Overall Endpoints

- Test failure rate, calculated as, tests not performed successfully providing an "unknown" or "fail" test result/ number of tests requested
- Mutation detection rate, calculated as performed successfully providing a "positive" mutation result / total number of successful tests providing a mutation result
- Testing success rate, calculated as, tests performed successfully providing a mutation result (positive/negative) / total number of tests requested

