13.2 Evaluable Population

The Evaluable Population consists of all enrolled patients with all non-missing or unknown:

- Tumour sample *EGFR* mutation test status.
- Tumour sample *EGFR* mutation test sub-type.
- Plasma *EGFR* mutation test status.
- Plasma *EGFR* mutation test sub-type.

Unless otherwise specified all summaries will be based on the Evaluable Population.

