14. METHOD OF STATISTICAL ANALYSIS

Descriptive summary of patient demographics and disease characteristics will be presented for all enrolled population and the evaluable population.

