14.2 Secondary Objectives

EGFR Mutation Frequency

The *EGFR* mutation frequency from the tumour sample in the evaluable population will be summarised overall and by country/region by adenocarcinoma and non-adenocarcinoma histologies.

First line treatment choice

 1^{st} line treatment choice following *EGFR* mutation testing will be summarised descriptively for the overall evaluable population by *EGFR* mutation status, *EGFR* mutation subtype and

by country/region.

Second line treatment choice

The percentage of patients on 2^{nd} line treatment, including treatment choice following discontinuation of first line treatment for patients confirmed as *EGFR* mutation positive via tissue/cytology will be summarised descriptively for the evaluable EGFR mutation positive population by *EGFR* mutation status, *EGFR* mutation subtype and by country/region. Treatment sequence i.e. 1^{st} line treatment choice and 2^{nd} line treatment choice will be summarised descriptively.

Summaries of EGFR mutation testing practices

The testing methodology, sample type and availability, testing turnaround time, testing success rate and mutation detection rate will be summarised using appropriate descriptive statistics for evaluable population. The reasons for testing not being performed will be listed.

Correlation between EGFR mutation status from tumour sample and demographic characteristics and disease status

The patient characteristics of the enrolled population will be compared to the characteristics of the evaluable population in order using summary statistics to understand any relationship between all aNSCLC patients and those whose samples undergo *EGFR* mutation testing.

The correlation between *EGFR* mutation status and both demographic characteristics and disease status will be analysed using a multivariate logistic regression model, constructed for the evaluable population to model *EGFR* tumour mutation status at baseline (*EGFR* mutation positive versus *EGFR* mutation negative from tumour sample) and key demographic characteristics such as histology (adenocarcinoma versus non-adenocarcinoma), smoking status (never- versus eversmoker) gender (female versus male), age (≤ 65 versus 65+) and WHO performance score (PS; 0-1, 2) and key disease status characteristics (time since diagnosis, disease stage at progression and number of organs with metastasis).

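### First-line therapy is recorded for all patients, but the planned summary covers only those with both tumour and plasma results, so treatment after an undetermined tumour test is never shown

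*Protocol*

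**What the plan says.** Collection is unrestricted. Section 2.1 states: "The first line therapy choice will be recorded for all patients". Only second-line therapy is limited there to tumour-positive patients.

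EGFR status has three recorded levels in Section 7.2. The third, unknown, is defined as EGFR "mutation status not determined as" positive or negative. The same section defines a test failure rate that counts unknown and failed results over tests requested, so such results are expected.

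The analysis is restricted. Under Section 14.2, first-line choice following EGFR "mutation testing will be summarised descriptively for the overall evaluable population by" mutation status, mutation sub-type and country or region. Section 13.2 defines the set: "The Evaluable Population consists of all enrolled patients with all non-missing or unknown", followed by four items (tumour status, tumour sub-type, plasma status, plasma sub-type). It adds a default: "Unless otherwise specified all summaries will be based on the Evaluable Population".

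The larger set has a narrow use. Section 14 says: "Descriptive summary of patient demographics and disease characteristics will be presented for all enrolled population and the evaluable population". Section 14.2 uses the Enrolled Population again only to compare patient characteristics. Table 4 asks for first-line choices by mutation status, country or region and sub-type, and names no other set.

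**The concern.** Secondary objective 2 is to describe first-line choice after EGFR testing. Unlike objective 3, it is not limited to patients with a particular result, and an undetermined result is one way in which testing can end. The study rationale is interested in the impact of the testing process and in whether patients are "treated appropriately on the basis of the molecular features of their disease". Patients for whom the tumour test gave no answer bear directly on that question. Their treatment is collected, and the plan then has no table in which it can appear.

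A second group is lost for a reason unrelated to the objective: patients with a clear tumour result whose plasma result is missing or unknown. They belong in the positive or negative column of the first-line table. The plasma requirement suits the concordance analysis, but objective 2 does not need it.

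**Working it through.** **1. How Section 13.2 must be read.** The phrase before the four items is ambiguous. Taken literally, it could keep patients whose result is unknown. But Section 14.1 uses the same set for sensitivity, specificity and predictive values, and Section 14.2 uses it for a logistic model of positive versus negative status. Both need a known status. The workable reading is that each item must be neither missing nor unknown.

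**2. Consequence for the table.** On that reading, the number of patients in the set with unknown tumour status is 0 at any failure rate. No other planned summary of treatment covers them.

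**3. Inputs.** Planned enrolment is N = 1300 (1000 Europe, 300 Japan; Section 2.1). The protocol gives neither the tumour unknown rate *u* nor the plasma failure rate *p*. Both are assumed below, and failures are taken as independent. The plan states no figure for this point. Its only design calculation, a 95% CI of 40-60% for a sensitivity of 50% in 100 positives, reproduces (Wald 40.2-59.8%, exact 39.8-60.2%) but has no bearing here.

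**4. Recorded first-line choices lost.**
- Unknown tumour status: N × u
- Tumour known, plasma not: N × (1 − u) × p
- Total: the sum of the two

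| u (assumed) | Unknown tumour | Total, p = 0% | Total, p = 5% | Total, p = 10% |
|---|---|---|---|---|
| 2% | 26 | 26 | 26 + 63.7 = 89.7 | 26 + 127.4 = 153.4 |
| 5% | 65 | 65 | 65 + 61.75 = 126.75 | 65 + 123.5 = 188.5 |
| 10% | 130 | 130 | 130 + 58.5 = 188.5 | 130 + 117 = 247 |
| 20% | 260 | 260 | 260 + 52 = 312 | 260 + 104 = 364 |

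**5. Effect on the positive and negative strata.** A patient with unknown tumour status is in neither stratum, so removing that patient changes no numerator or denominator there. The plasma requirement is different. Within a stratum, let *a* be the share given a certain treatment among patients with a plasma result, and *b* the share among those without.
- Share in the whole stratum: (1 − p)a + pb
- Share the plan would report: a
- Shift: a − [(1 − p)a + pb] = p(a − b)

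Since a and b lie between 0 and 1, the shift is at most p in size: 5 percentage points at p = 5%, 10 at p = 10%. It is zero if a = b, and the protocol gives no information on a − b or its sign. The loss of precision is small: interval widths grow by about 1/√(1 − p), that is 1/√0.95 = 1.026 or 1/√0.90 = 1.054.

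**The case against.** The strongest reply is that the outcome in Table 4 is stratified by mutation status. Unknown-status patients never enter the positive or negative columns, so those percentages are the same with or without them. This is correct. A reader might infer that the plan makes testing look as if it steers treatment better than it does, or that the study will report every first-line choice as made with a known mutation status. The documents support neither. No section plans or states a share of choices made with known status, and the stratified figures are not moved by leaving the unknowns out.

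Two further replies have some force. The wording of Section 13.2 is ambiguous, so the exclusion is an interpretation. It is, however, the only one compatible with the analyses in Sections 14.1 and 14.2, and the sentence needs rewording either way. The size is also assumed: at 2% unknown, the gap concerns 26 of 1300 patients in a descriptive secondary table.

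It might also be said that a statistical analysis plan could add the missing table. But the protocol does not leave the set open. Section 14.2 names it, and a plan that follows the protocol inherits the exclusion.

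What remains is that recorded data which objective 2 calls for have no planned summary, and that patients with a known tumour result are removed from its strata for want of a plasma result.

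**Conclusion.** The point holds as a gap in reporting. As written, objective 2 is answered only for patients in whom both tests succeeded. Treatment after an undetermined tumour test cannot appear, whatever its frequency. That conclusion rests on the workable reading of Section 13.2 and on no assumed rate.

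The number of patients affected does rest on assumptions: 26, 65 or 130 of 1300 at 2%, 5% or 10% unknown tumour status, rising to 247 if 10% of plasma tests fail as well as 10% of tumour tests. At the outer limit considered (20% and 10%) it is 364.

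Bias in the positive and negative columns is possible only through the plasma requirement. It is bounded by the plasma failure rate within the stratum and is not demonstrated. The primary concordance analysis is untouched, and the study tests no hypothesis. This is a secondary point, worth correcting because the correction is nearly free.

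**What to change.** - In Section 14.2 and Table 4, summarise first-line choice in the existing Enrolled Population, among patients with recorded first-line data. Tabulate by tumour status positive, negative and unknown, and by country or region, without conditioning on the plasma result.
- Keep the mutation sub-type split for tumour-positive patients.
- Reword Section 13.2 so that each of the four items must be *neither missing nor unknown*.

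The cost is one extra table column and a denominator that differs from that of the primary analysis, which a table footnote can explain. No new analysis set is needed, and no new data, because therapy is already recorded for all patients.

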1.2 Secondary objectives

Secondary objectives of the study are:

- 1. To determine the *EGFR* mutation frequency (including mutation subtypes) in patients with advanced NSCLC (aNSCLC) of adenocarcinoma and non-adenocarcinoma histologies.
- 2. To describe first line therapy choice following *EGFR* mutation testing.
- 3. To describe second line therapy choice following discontinuation of first line treatment for patients confirmed as *EGFR* mutation positive via tissue/cytology.
- 4. To summarise *EGFR* mutation testing practices in terms of methods, sample types, success rate, mutation detection rate, testing turnaround time and reasons for not testing.
- 5. To determine the correlation between *EGFR* mutation status from tumour and demographic data and disease status.
- 6. To determine the correlation between *EGFR* mutation status derived from plasma (blood) and demographic data and disease status.

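### The percentage on second-line treatment is summarised over all evaluable mutation-positive patients, with no first-line stop date or status listed and no cut-off fixed, so it cannot be read as uptake after first-line discontinuation

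*Protocol*

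**What the plan says.** Secondary objective 3 (Protocol Section 1.2) is conditional on stopping first line: "To describe second line therapy choice following discontinuation of first line treatment for patients confirmed as" EGFR mutation positive on tissue or cytology. Section 2.1 sets the same trigger for data entry: "The second line therapy choice will be recorded following discontinuation of first line treatment".

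The analysis in Section 14.2 is "The percentage of patients on 2^{nd} line treatment, including treatment choice following discontinuation of first line treatment", and it is to be "summarised descriptively for the evaluable EGFR mutation positive population", broken down by mutation subtype and country/region. Table 4 in Section 12.1 also lists the percentage on second-line treatment as an outcome, beside treatment sequence and second-line choices. Neither place restricts the percentage to patients who have stopped first line.

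Section 7.2 gives the data to be collected for the secondary objectives. The first-line entry ("line treatment decision after testing") and the second-line entry each contain treatment name, start date and reason for choice. The only treatment date listed for either line is "Treatment start date".

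On timing, Section 2.1 says "Patients will be recruited over approximately 18 months". The study plan (Table 1) has a single post-testing column, to be filled as data come in, with no follow-up duration or closing date. Section 4.2 ends data collection when a patient leaves the study.

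**The concern.** The objective asks what happens after first line stops, but the stated population includes patients who have not stopped. Read naturally, a patient still on first line when the database closes counts as not on second line.

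The listed variables do not allow this to be undone. Anyone who starts second line is identifiable from the second-line entry. A mutation-positive patient without that entry could be still on first line, off treatment, dead or lost, and nothing in Section 7.2 or Table 1 separates these states. An analysis plan can choose a different denominator, but it cannot recover a stop date or status that was never captured.

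At stake is how one secondary outcome is interpreted, and its planned breakdowns in particular. Groups with the same uptake after stopping could show different percentages only because they were enrolled at different times or stayed on first line for different periods.

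**Working it through.** The protocol gives no expected second-line percentage, time on first line or follow-up length, so it has no figure of its own to reproduce here. The calculation below only illustrates sensitivity.

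**Inputs**
- Recruitment period: 18 months (Section 2.1). Uniform entry is assumed.
- F, months from last enrolment to data cut-off: not stated; 0 to 24 assumed.
- m, median time on first line: not stated; exponential with 10 months assumed, range 6 to 14.
- q, share of stoppers who start second line, taken as immediate: not stated; 60% and 70% assumed, range 40% to 80%.

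**Formula.** With L = ln2/m, the share of patients who have stopped first line by the cut-off is

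S = 1 - exp(-L·F) × (1 - exp(-18L))/(18L).

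The percentage over all mutation-positive patients is q × S.

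**Numbers for m = 10.** L = 0.0693 and 18L = 1.248, so (1 - 0.287)/1.248 = 0.571. At F = 0, S = 1 - 0.571 = 0.429. At F = 12, S = 1 - 0.435 × 0.571 = 0.751.

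| F (months) | Share stopped | q = 60% | q = 70% |
|---|---|---|---|
| 0 | 42.9% | 26% | 30% |
| 6 | 62.3% | 37% | 44% |
| 12 | 75.1% | 45% | 53% |
| 24 | 89.2% | 54% | 62% |

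**Other medians, q = 60%.** From F = 0 to F = 24 the figure runs from 35% to 58% with m = 6, and from 20% to 48% with m = 14.

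**Follow-up against uptake.** With m = 10 and q = 60%, moving the cut-off from 0 to 24 months shifts the figure from 26% to 54%. With the cut-off held at 6 months, doubling q from 40% to 80% shifts it from 25% to 50%. Over these ranges the two have about the same influence.

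**Comparisons between groups, q = 60% in both.**
- Follow-up of 6 or 18 months per patient, m = 10: shares stopped are 1 - 2^(-6/10) = 0.340 and 1 - 2^(-18/10) = 0.713, giving 20% and 43%.
- Medians of 6 or 14 months on first line, cut-off at F = 6: shares stopped are 0.790 and 0.508, giving 47% and 30%.

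In this model the proportion among stoppers equals q at every cut-off. That follows from holding q constant. If uptake differs between early and late stoppers, a short cut-off also distorts the proportion among stoppers.

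**The case against.** The strongest reply is that the denominator is inferred. Section 14.2 names an analysis set and, in the same sentence, refers to discontinuation of first line; Table 4 fixes no denominator. Choosing one is ordinary SAP content, and the SAP is not at hand. This stands for the denominator alone. It does not answer the missing stop date or status, because Section 7.2 sets out what is collected for these objectives.

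The eCRF is not shown either, and sites must recognise first-line discontinuation to know when to record second line. Patients leaving the study are asked why (Section 4.2), so some losses may be identifiable. The supportable claim is therefore that the protocol does not list these items, not that no site will hold them.

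The objective itself concerns the choice of treatment. The distribution of second-line choices and the treatment sequence rest on patients who started second line and do not use the disputed denominator, although a short cut-off weights them towards early stoppers. This stands and narrows the point to the percentage.

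The share of mutation-positive patients who have reached second line is also a legitimate descriptive quantity. That is so, but it needs a stated follow-up to mean anything, and none is given.

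A reader might go further and infer that the percentage mostly measures follow-up length, or that it falls short of a known true uptake. The documents support neither. The figure mixes follow-up, time on first line and uptake, and the protocol gives no value for uptake. With a cut-off 24 months after last enrolment and q = 60%, the figure comes within about 2 to 12 points of the value among stoppers (58% for m = 6, 48% for m = 14).

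**Conclusion.** The point holds in limited form. As written, the percentage on second-line treatment depends heavily on follow-up and on time on first line. It cannot be read as uptake after first-line discontinuation, and its breakdowns by country/region and mutation subtype are not clean comparisons.

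The size is illustrative and rests wholly on the assumed entry pattern, exponential time on first line and constant uptake: about 26-30% at the end of recruitment and 45-53% twelve months later, for 60-70% uptake among stoppers and a 10-month median. Nothing in the protocol places the cut-off at the end of recruitment, and no staggering of recruitment between countries is documented. Longer follow-up would shrink the gap, but none is guaranteed.

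This affects one descriptive outcome under one of six secondary objectives, in a study without hypothesis tests. The primary concordance analysis is untouched. It is a cheap improvement that should be made, and best made before data capture closes because omitted dates are harder to recover later.

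**What to change.** In Section 7.2 and the eCRF, add first-line stop date or current status, and date of last contact or death. State the data cut-off.

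In Section 14.2, report second-line starts among patients known to have discontinued first line. Keep in that denominator those who stopped and then died or had no further treatment, and show those still on first line or lost separately.

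A simple proportion among known stoppers over-represents early stoppers when the cut-off is short. So also report follow-up duration and a cumulative incidence of starting second line, with death as a competing event.

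The cost is two or three extra eCRF fields, which should be available from routine records, and a little more analysis. Only data capture and analysis change; patient management does not.

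### Testing success rate is to be summarised in a population that admits only patients with known tumour and plasma results, so at patient level it is 100% whatever the true rate

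*Protocol*

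**What the plan says.** **The endpoint.** Section 7.2 defines it as "Testing success rate, calculated as, tests performed successfully providing a mutation result (positive/negative) / total number of tests requested". The failure rate has the same denominator and counts unknown or failed results in the numerator. An unknown status is one with "mutation status not determined as" either positive or negative.

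**The population.** For testing practice, section 14.2 says that "testing success rate and mutation detection rate will be summarised using appropriate descriptive statistics for evaluable population". Methodology, sample type and availability, and turnaround time stand in the same sentence. Section 13.2 opens with "The Evaluable Population consists of all enrolled patients with all non-missing or unknown" and then lists four items: tumour status, tumour sub-type, plasma status and plasma sub-type. It adds a default: "Unless otherwise specified all summaries will be based on the Evaluable Population".

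**Failure rate and reasons for not testing.** Section 14.2 does not name the failure rate. It says that the reasons for not testing will be listed, and names no population for the listing. Table 4 in section 12.1 describes the same reasons as summarised.

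**The wider set.** Section 13.1 defines an Enrolled Population of all consenting patients. Section 14 uses it only for demographics and disease characteristics.

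**Tumour-only outcomes.** These are restricted in the same way. For example, the "mutation frequency from the tumour sample in the evaluable population will be summarised overall and by country/region".

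**The concern.** A success rate has to be taken over a set that contains the failures. Here the analysis set is defined by having a result, so it leaves out the events that the endpoint is meant to count. Secondary objective 4 asks how EGFR testing works in practice, including how often it succeeds and why it is not done. The study rationale also gives the current state of testing as an aim. A reported 100% would look like a finding about practice in Europe and Japan when it only restates the definition of the population. Sample availability, in the same sentence of section 14.2, is affected in the same way.

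The protocol fixes this choice explicitly. It is not a detail left open for an analysis plan, and a plan that followed the protocol would inherit it.

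**Working it through.** The protocol states no success or failure figure, so there is nothing of its own to reproduce. The check is logical first and then illustrative.

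**Step 1: patient level.** Success = "tests performed successfully providing a mutation result (positive/negative) / total number of tests requested". Every patient in the Evaluable Population has a positive or negative tumour result and a positive or negative plasma result. Counting one final test per patient and sample type, success = n/n = 100% and failure = 0/n = 0%. This needs no assumption about failure rates.

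**Step 2: how many patients are removed.** Inputs:
- N = 1300 (1000 Europe, 300 Japan), from section 2.1.
- Tumour failure probability ft and plasma failure probability fp are not in the protocol. Assumed: ft = 2-20%, fp = 2-10%, independent, with one test requested per sample type and patient.

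Evaluable n = N(1 - ft)(1 - fp). True success is 1 - ft for tumour and 1 - fp for plasma.

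| ft | fp | Evaluable n | Removed | True success, tumour / plasma | Reported |
|---|---|---|---|---|---|
| 2% | 2% | 1300 × 0.98 × 0.98 ≈ 1249 | 51 | 98% / 98% | 100% / 100% |
| 10% | 5% | 1300 × 0.90 × 0.95 ≈ 1112 | 188 | 90% / 95% | 100% / 100% |
| 20% | 10% | 1300 × 0.80 × 0.90 = 936 | 364 | 80% / 90% | 100% / 100% |

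Independence affects only the number removed. The 100% does not depend on it.

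**Step 3: test level, with repeats.** Suppose a first test fails with probability f, a failure is repeated once with probability q, and the repeat succeeds with probability 1 - f.
- All tests: success = (1 - f)(1 + fq) / (1 + fq) = 1 - f.
- Evaluable patients only: success = (1 - f)(1 + fq) / [(1 - f)(1 + 2fq)] = (1 + fq) / (1 + 2fq).

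With f = 10%, where the true rate is 90.0%:
- q = 0: 100%.
- q = 0.5: 1.05 / 1.10 = 95.5%.
- q = 1: 1.10 / 1.20 = 91.7%.

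The bias shrinks as more failures are repeated, but it does not disappear even when all are repeated once.

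**Step 4: which items reach this set, and how.** Success rate, detection rate, methods, sample type and availability, and turnaround are placed there by section 14.2 itself. The failure rate arrives only through the default in section 13.2. The reasons for not testing arrive only if the listing counts as a summary, as Table 4 suggests.

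**Step 5: tumour-only outcomes.** Patients with a known tumour status who are lost because plasma is missing or failed number N(1 - ft)fp. Over the assumed ranges this is from 1300 × 0.80 × 0.02 ≈ 21 to 1300 × 0.98 × 0.10 ≈ 127. Confidence intervals for a proportion widen by a factor of about 1/√(1 - fp), which is 1.01 at 2% and 1.05 at 10%.

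**The case against.** **The definition of the population is unclear.** Section 13.2 is badly worded, and section 14.2 uses the term loosely elsewhere. It speaks of evaluable patients with available plasma samples, and it treats evaluable patients as those whose samples were tested, which is not the same as tested with a result. This is fair, and the 100% does rest on reading 13.2 as neither missing nor unknown. But a reading that admits unknown results would put undetermined results into the concordance and sensitivity tables of section 14.1, and it would still exclude missing or unperformed tests. The alternative does not work.

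**The endpoint is per test.** This stands. The exact 100% is a patient-level statement, and step 3 shows lower values where tests are repeated. The direction of the bias does not change.

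**The rest of objective 4 survives.** A reader might infer that the whole objective cannot be answered. The protocol does not support that. Methods, sample types and turnaround can be estimated, though only among patients with both results. The detection rate already has successful tests as its denominator.

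**The reasons listing need not be empty.** A reader might also infer that it must be. Section 14.2 names no population for it, and a listing is arguably not a summary. Given the default and Table 4, it could be empty; that is as far as the text goes.

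**One common set is a legitimate choice for tumour-only outcomes.** Plasma is mandatory, and enrolled and evaluable patients are to be compared on their characteristics. No bias in tumour-only results has been shown. What remains is an avoidable loss of precision.

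**Conclusion.** The concern holds for the success and failure rates. As written, section 14.2 gives a patient-level success rate of 100% for tumour and for plasma regardless of what happened, and an upward-biased rate at test level. That part of secondary objective 4 is uninformative. Sample availability shares the problem. The other testing-practice items are estimable in a selected set, and the population for the reasons for not testing has to be stated.

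The size rests on assumed failure rates, because the protocol gives none. With independent failure of 2-20% for tumour and 2-10% for plasma, 51 to 364 of 1300 patients are removed, and 100% is reported in place of 80-98% and 90-98% respectively. The logical result rests only on reading section 13.2 as neither missing nor unknown.

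The primary concordance analysis is not affected by this point; it needs both results. The restriction of tumour-only outcomes is secondary: a modest loss of precision, with no demonstrated bias.

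**What to change.** - **Section 14.2, testing practices:** compute success, failure, availability, methods, turnaround and reasons for not testing in the Enrolled Population, separately for tumour and plasma. Use tests requested as the denominator for the success and failure rates, as section 7.2 already defines them, and name the failure rate.
- **Reasons for not testing:** state the population, and make section 14.2 and Table 4 agree on whether they are listed or summarised.
- **Section 13.2:** reword the condition as neither missing nor unknown, keep that set for concordance, and amend the default so that it no longer captures the testing-practice endpoints.
- **Optional gain in precision:** compute tumour mutation frequency, treatment choice by tumour status and the tumour regression in all enrolled patients with a known tumour status, regardless of plasma.

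The cost is wording in sections 13.2, 14.2 and Table 4. No new data are needed, since section 7.2 already collects test results, sample availability and reasons for not testing. The downside of the optional change is that denominators in the tumour-only tables would differ from the concordance set, so each table should state its own.
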